3.6 Study Procedures

Study procedures are outlined in the Schedule of Events ([Table 2](#)); selected procedures are described thereafter.

Forma

Trevena, Inc.

Protocol CP130-3003

Version 5.0

14 Sep 2016

Table 2: Schedule of Events

Procedures	Screening phase ¹ (≤ 14 days before first dose of oliceridine)	Baseline phase ¹ (Day 1)	Treatment phase (up to 14 days)		End-of-treatment phase ²				Follow-up phase ³ (Between 2 days and 3 days after completion of treatment phase)
			Predose (Day 1)	T0 to last dose of oliceridine ⁴	End-of-treatment documentation ²	Within 1 hour after completion of treatment phase ²	Within 3 hours after completion of treatment phase ²	One day after completion of treatment phase	
Informed consent ⁵	X								
Demographics	X								
Medical history	X	X							
Eligibility criteria	X	X							
ASA physical status classification ⁶	X	X							
ESI ⁷	X								
Physical examination ²	X	X			X				
Clinical laboratories ⁸	X	X					X		
Blood sample for future CYP2D6 genotyping				X					
Urine or serum pregnancy test ⁹	X	X							
Urine or serum toxicology screen ¹⁰	X								
Weight	X	X							
Height ¹¹	X								
ECG	X	X	X ¹²	X ¹³					
PK sampling ¹⁴				X					
PCA patient training ¹⁵	X	X	X	X					
Oliceridine dosing				X					
NPRS ¹⁶		X	X	X		X			
Vital signs ¹⁷	X	X	X	X		X			
MRPSS ¹⁸			X	X		X			
SOWS ¹⁹								X	
Oxygen saturation ²⁰			←-----X-----→						
Prior, concomitant medications ²¹	←-----X-----→		←-----X-----→						
AE/SAE reporting ²²	←-----X-----→								

Confidential

Page 37 of 67

Trevena, Inc.

Protocol CP130-3003

Version 5.0

14 Sep 2016

Abbreviations: AE = adverse event; ASA = American Society of Anesthesiologists; CYP2D6 = cytochrome P450 2D6; ECG = electrocardiogram; ESI = Emergency Severity Index; MRPSS = Moline-Roberts Pharmacologic Sedation Scale; NPRS = Numeric Pain Rating Scale; PCA = patient-controlled analgesia device; PK = pharmacokinetic; SAE = serious adverse event; SOWS = Subjective Opiate Withdrawal Scale; T0 = time of first oliceridine dose.

1. When screening and baseline procedures are anticipated to occur within 48 hours of each other, they may be executed as a single procedure, unless the clinical condition of the patient has significantly changed since screening.
2. When the investigator documents that the last dose of oliceridine was administered and that the patient will no longer be treated with oliceridine, the treatment phase is complete and the end-of-treatment phase begins. A physical examination will be performed at this time.
3. Follow-up contact may be conducted in person or by telephone.
4. Procedures will be performed at any and all times during the dosing period consistent with individual patient need and institutional standards of care for a patient receiving a parenteral opioid.
5. Written informed consent.
6. If a surgical or medical patient. Refer to Section 9.3 for the ASA scale.
7. If an ED patient. Refer to Section 9.4 for the ESI scale.
8. Blood chemistry and hematology will be obtained using local laboratories and local laboratory range values.
9. Female patients of childbearing potential only.
10. If an ED patient.
11. Height may be obtained by measurement or patient attestation.
12. During the predose period, an additional, post-surgical ECG will be performed only in surgical patients.
13. ECG will be obtained during the Treatment Phase at 60 minutes after the first dose of oliceridine, and at every 24 hours of oliceridine treatment.
14. PK samples will be collected at two times during the treatment phase: sample 1 at 30 minutes (+/- 10 minutes) after the first dose; sample 2 between 1 and 2 hours after the first dose. Unscheduled PK samples may be required. Refer to Sections 3.5.2.3 and 3.6.3.
15. PCA patient training is required before PCA use. If PCA is planned, training will occur during the screening and baseline phases; if PCA is started during the treatment phase, training will occur before PCA use. Training is repeated according to patient need.
16. NPRS will be measured during the predose period, at 30 minutes +/-10 minutes after the first dose of oliceridine, and at any and all times during the dosing period consistent with individual patient need and institutional standards of care for a patient receiving a parenteral opioid (see Section 9.2).
17. Blood pressure, heart rate, respiratory rate, and temperature. Temperature will be measured at screening and baseline only.
18. Refer to Section 9.1 for the MPRSS.
19. Refer to Section 9.5 for the SOWS. If the patient is discharged or transferred before the time when the SOWS is to be performed, it will be performed one day after completion of the treatment phase and returned to the site by mail or in person.
20. Oxygen saturation monitoring will be continuous but will be recorded at any and all times during the dosing period consistent with individual patient need and institutional standards of care for a patient receiving a parenteral opioid. The date and time of initiation and discontinuation of continuous oxygen saturation monitoring will be recorded in the source documents.
21. Prior medications are defined as those taken before the first dose of oliceridine. Concomitant medications are defined as those taken after the first dose of oliceridine. Prior medications taken or administered within the 14 days before the first dose of oliceridine will be recorded in source and will also be recorded in eCRF. Supplemental oxygen will be recorded as a prior and/or concomitant medication.
22. AEs occurring from time of informed consent to the follow-up phase will be recorded in source and will also be recorded in eCRF if the patient receives oliceridine. SAEs occurring from time of informed consent to the follow-up phase or 7 days after the last dose of oliceridine (whichever occurs later) will be recorded in source and eCRF; ongoing SAEs after this time frame will be followed until the investigator, medical monitor, and sponsor agree that the SAE is satisfactorily resolved. SAEs considered by the investigator to be related to oliceridine, regardless of the time of onset after treatment, should be reported.

3.6.1 Screening and Baseline Procedures

- When screening and baseline procedures are anticipated to occur within 48 hours of each other, they may be executed as a single procedure, unless the clinical condition of the patient has significantly changed since screening.
- For this study, AE reporting begins from time of informed consent.
- Height without shoes will be measured or obtained by patient attestation and recorded in inches. Weight without shoes will be measured and recorded in pounds.
- Urine or serum pregnancy test will be performed on female patients of childbearing potential only. Tests obtained before informed consent may be used as study data if obtained within 24 hours before the first dose of oliceridine or obtained during the current ED visit.
- Standard, 12-lead ECG will be captured using local equipment. Tests obtained before informed consent may be used as study data if obtained within 14 days before the first dose of oliceridine or obtained during the current ED visit.
- PCA patient training is required before PCA use. If PCA is planned, training will occur during the screening and baseline phases; if PCA is started during the treatment phase, training will occur before PCA use. Training is repeated according to patient need.
- American Society of Anesthesiologists (ASA) Physical Status Classification System score (if a surgical or medical patient); if an ED patient, Emergency Severity Index (ESI) triage score (if an ED patient) (see Sections 9.3 and 9.4).
- If an ED patient, urine or serum toxicology screen. Test results obtained before informed consent may be used as study data if obtained during the current ED visit.
- Clinical laboratories include blood chemistry and hematology. These will be obtained using local laboratories and local laboratory range values. Tests obtained before informed consent may be used as study data if obtained within 14 days before the first dose of oliceridine or obtained during the current ED visit.
- Physical examinations will include examination of general appearance, skin, neck (including thyroid), eyes, ears, nose, throat, heart, lungs, abdomen, lymph nodes, extremities, and nervous system.

3.6.2 Safety and Tolerability Procedures

The safety and tolerability of oliceridine will be assessed through self-reported or observed AEs, vital sign measurements, oxygen saturation measurements, somnolence/sedation scores, physical

Trevena, Inc.

Protocol CP130-3003

Version 5.0

14 Sep 2016

examination findings, clinical laboratory assessments, and the subjective opiate withdrawal scale (SOWS).

3.6.2.1 Adverse Events

AEs occurring from time of informed consent to the follow-up phase will be recorded in source and will also be recorded in eCRF if the patient receives oliceridine. SAEs occurring from time of informed consent to the follow-up phase or 7 days after the last dose of oliceridine (whichever occurs later) will be recorded in source and eCRF; ongoing SAEs after this time frame will be followed until the investigator, medical monitor, and sponsor agree that the SAE is satisfactorily resolved. SAEs considered by the investigator to be related to oliceridine, regardless of the time of onset after treatment, should be reported.

AE reporting information is provided in [Section 4](#).

3.6.2.2 Vital Signs, Height, Weight

Vital signs will include blood pressure (BP), heart rate (HR), respiratory rate (RR), and temperature. Temperature will be measured at screening and baseline only.

3.6.2.3 Oxygen Saturation

Oxygen saturation monitoring will be continuous but will be recorded at any and all times during the dosing period consistent with individual patient need and institutional standards of care for a patient receiving a parenteral opioid. The date and time of initiation and discontinuation of continuous oxygen saturation monitoring will be recorded in the source documents.

3.6.2.4 Somnolence/Sedation

The MRPSS will be used to measure somnolence/sedation ([Moline, 2012](#)). This scale was developed to measure pharmacologic sedation in non-ICU patients, rather than many sedation scales that measure goal-directed sedation. Six levels describe the range of sedation from “non to minimal” to “general anesthesia”. Additionally, normal sleep is integrated into these levels, as opposed to being positioned as a separate category, easing quantitative analysis ([Moline, 2012](#)) ([Pasero, 1994](#)).

3.6.2.5 Physical Examination

The physical examination will include general appearance, skin, neck (including thyroid), eyes, ears, nose, throat, heart, lungs, abdomen, lymph nodes, extremities, and nervous system. Clinically significant changes from screening/baseline in the physical examination for a surgical or medical patient will not be recorded as AEs unless they are of greater severity and/or intensity than would be expected.

Trevena, Inc.

Protocol CP130-3003

Version 5.0

14 Sep 2016

3.6.2.6 Clinical Laboratories

Clinical laboratories include blood chemistry and hematology obtained using local laboratories and local laboratory range values.

Chemistry includes: Albumin, total bilirubin, total protein, calcium, alkaline phosphatase, alanine aminotransferase (ALT), aspartate aminotransferase (AST), blood urea nitrogen (BUN), creatinine, glucose, sodium, potassium, chloride, bicarbonate, lactate dehydrogenase, and uric acid.

Hematology includes: hemoglobin, hematocrit, red blood cell (RBC) count, RBC indices, mean corpuscular hemoglobin (MCH), mean corpuscular hemoglobin concentration (MCHC), platelet count (or estimate), and white blood cell (WBC) count including differential.

Urine or serum toxicology includes any standard of care analytes at the institution where the study is being conducted.

3.6.2.7 Subjective Opiate Withdrawal Scale

Patients will be monitored for symptoms and signs of opioid withdrawal. Acute opioid withdrawal reflects μ opioid receptor upregulation: pain, autonomic hyperactivity, bowel hypermotility, temperature instability, and psychological symptoms. Subjective symptoms may include physical symptoms (e.g., myalgias, nausea, diarrhea, chills) and psychological symptoms (e.g., cravings, insomnia, fatigue). Objective signs may include: tachycardia, hypertension, tearing, runny nose, yawning; vomiting; sweating, piloerection; agitation and restlessness.

The SOWS will be administered to detect symptoms of opioid withdrawal ([Handelsman, 1987](#)). Patients will score each of 16 symptoms on an intensity scale ranging from 0 (“not at all”) to 4 (“extremely”).

3.6.3 Pharmacokinetic Procedures

PK samples will be collected at two times during the treatment phase:

- Sample 1 at 30 minutes (+/- 10 minutes) after the first dose;
- Sample 2 between 1 and 2 hours after the first dose.

For all samples, the actual sampling time will be recorded. Drug plasma concentration data collected in this study and detailed dosing times for each patient will be incorporated into a previously developed PK model in order to predict each individual’s oliceridine exposure.

In addition to the scheduled PK sampling, an unscheduled PK sample will be obtained under the following circumstances:

- If a patient reaches the dosing limit of 60 mg in the first 12 hours (see [Section 3.5.2.3](#))

Trevena, Inc.

Protocol CP130-3003

Version 5.0

14 Sep 2016

- If a patient experiences a serious AE or a severe AE during the treatment phase. As the determination of a serious AE or a severe AE is sometimes retrospective, unscheduled PK samples obtained when an event that is suspected to be serious or severe are also permitted.

3.6.4 Efficacy Procedures

Analgesic efficacy will be measured using NPRS (see Section 9.2) at the following time points:

- During the predose period.
- 30 minutes +/-10 minutes after the first dose of oliceridine.
- At any and all times during the dosing period consistent with individual patient need and institutional standards of care for a patient receiving a parenteral opioid.

3.6.5 Other Procedures

A blood sample will be collected for future 2D6 genotyping. The sample will be collected after the first dose of oliceridine and before the conclusion of the end of treatment phase. It is recommended that this sample be collected at the time of the first PK sample.

4 ADVERSE EVENT REPORTING

The investigator and study staff are responsible for detecting and recording AEs and SAEs, during scheduled safety and tolerability evaluations and whenever such information is brought to their attention. This section of the protocol provides definitions and detailed procedures to be followed.

During each visit, the investigator will question a patient about AEs using an open-ended question approach, making sure not to influence that patient's answers, eg, "Have you noticed any change in your health?" or "How do you feel?."

4.1 Definitions and Criteria

4.1.1 Adverse Events

An AE is any untoward medical occurrence in a study patient that is temporally associated with the use of a medicinal product, regardless of its potential relationship to the medicinal product. An AE, therefore, can be any unfavorable or unintended sign, including a clinically significant abnormal laboratory finding, symptom, or disease temporally associated with the use of the IP, whether or not it is considered to be IP related. This includes any newly occurring event or previous condition that has increased in severity or frequency from time of informed consent.

Examples of an AE include:

- Exacerbation of a pre-existing condition, including either an increase in frequency and/or intensity of the condition.
- A new condition detected or diagnosed.
- Signs or symptoms of a drug interaction.
- Signs or symptoms of a suspected overdose of either IP or a concurrent medication (overdose per se should not be reported as an AE/SAE).
- A new laboratory abnormality that results in patient withdrawal from the study or medical treatment or further follow-up.

NOTE: abnormal laboratory values obtained during screening that preclude a patient from entering the study are not considered AEs, but they will be recorded.

AEs may include pre- or post-treatment events that occur as a result of protocol-mandated procedures (ie, invasive procedures, modification of patient's previous therapeutic regimen).

Symptoms or signs anticipated for a surgical or medical patient will not be recorded as AEs unless they are of greater severity and/or intensity than would be expected. Investigators will use

Trevena, Inc.

Protocol CP130-3003

Version 5.0

14 Sep 2016

their clinical judgment in determining whether the symptoms or signs are of greater severity and/or intensity than would be expected.

A medical intervention to address an AE is an “action taken” and not an AE in itself.

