1 INTRODUCTION

1.1 Background

Inadequately treated pain has significant short- and long-term consequences, including prolonged emergency department stays, psychological disturbances, and dissatisfaction with medical care. Opioid analgesics like morphine, fentanyl, and hydromorphone are mainstays of acute pain management; however, their use is hampered by well-known adverse events (AEs), such as respiratory depression, nausea, vomiting, and sedation (Lubawski, 2008) (Philip, 2002). Ultimately, the unmet medical need in acute pain therapy is an increased level of efficacy with acceptable tolerability.

Beta-arrestin knock-out animals treated with morphine were shown to experience improved analgesic efficacy, less respiratory depression and less constipation, compared with wild-type animals (Bohn, 1999) (Raehal, 2005). This led to the hypothesis that analgesia and AEs are mediated by two distinct signaling pathways distal to the μ -opioid receptor and that a selective μ -opioid receptor ligand that stimulates G protein signaling without stimulating β -arrestin recruitment could be a better analgesic.

Oliceridine selectively binds to the μ -opioid receptor with high affinity; however, oliceridine is a G protein biased ligand at the μ -opioid receptor in that it stimulates G protein signaling without stimulating β -arrestin recruitment. In preclinical species, this biased signaling profile has led to potent analgesic efficacy, with less respiratory depression, slowing of gastrointestinal motility, and sedation, compared with morphine.

To date, oliceridine has been evaluated in phase 1 and 2 clinical studies. A total of 185 healthy subjects have received single intravenous (IV) infusions of oliceridine (0.15 mg to 7 mg), and 40 healthy subjects have received multiple IV infusions (≤ 4.5 mg every 6 hours; 4 mg every 4 hours) in phase 1 studies. At those doses, oliceridine was generally well tolerated. The most commonly reported AEs included dizziness, nausea, somnolence, and feeling hot.

A total of 296 patients have received IV infusions of oliceridine (0.5 mg to 4 mg) in two phase 2 studies. At those doses, oliceridine was generally well-tolerated. The most commonly reported AEs were nausea, dizziness, vomiting, and headache.

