1.3 Study Endpoints

1.3.1 Safety and Tolerability Endpoints

The safety and tolerability of oliceridine will be measured as the incidence of self-reported or observed AEs, including those related to vital sign measurements, oxygen saturation measurements, somnolence/sedation scores, physical examination findings, and clinical laboratory assessments. Somnolence/sedation will be measured using the Moline-Roberts Pharmacologic Sedation Scale (MRPSS; see Section 9.1) ([Moline, 2012](#)). The MRPSS is designed to provide a consistent method of assessing pharmacologic sedation and assist in the decision-making process regarding the administration of opioids, sedatives, and other agents which produce sedation. For patients receiving a parenteral opioid in current practice, intensive monitoring is the standard of care. This monitoring will be used in the current study to evaluate

Trevena, Inc.

Protocol CP130-3003

Version 5.0

14 Sep 2016

oliceridine. Protocol-specified patient monitoring is compatible with the Joint Commission Sentinel Event Alert for the safe use of opioids in hospitals ([The Joint Commission, 2012](#)).

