4.2 Reporting Procedures and Requirements

4.2.1 Adverse Events

AEs occurring from time of informed consent to the follow-up phase will be recorded in source and will also be recorded in eCRF if the patient receives oliceridine. All AEs must be recorded irrespective of whether they are considered medication-related. All AEs that are potentially related to IP will be followed until resolution or database lock, whichever occurs first. This includes any newly occurring event or previous condition that has increased in severity or frequency from time of informed consent.

Any AEs already documented at a previous assessment and designated as ongoing should be reviewed at subsequent visits as necessary. If these have resolved, this should be documented. Changes in intensity or frequency of AEs should be recorded as separate events (ie, a new record started).

The investigator should report all AEs on the AE page(s) of the eCRF and source documents, regardless of seriousness, severity, and causality. Whenever possible, an AE will be reported using a diagnostic term, (eg, “common cold” or “upper respiratory infection” rather than “runny nose, cough, mild fever”) and should be described with the attributes described in [Section 4.1](#).

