6.3.6 Physical Examination

The physical examination will include general appearance. Results from screening/baseline will be recorded as medical history events while changes from screening/baseline in the physical examination will be recorded as AEs. The investigator will exercise his or her medical and scientific judgment in deciding whether an abnormal finding is clinically significant.

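### The AE definition lets investigators leave anticipated symptoms of ordinary severity unrecorded, with no carve-out for opioid effects, so TEAE incidence can be understated

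*Protocol*

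**What the plan says.** Protocol 1.3.1 sets the measure for the primary objective: "The safety and tolerability of oliceridine will be measured as the incidence of self-reported or observed AEs". SAP 8.6.3 reports it as TEAEs: overall, by severity, by relationship, by preferred term, and repeated by subgroup, including initial setting.

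Protocol 4.1.1 then narrows what counts: "Symptoms or signs anticipated for a surgical or medical patient will not be recorded as AEs unless they are of greater severity", or greater intensity, than expected. Investigators are to use "their clinical judgment in determining whether the symptoms or signs are of greater severity and/or intensity than would be expected". Neither the anticipated symptoms nor a reference severity is given. Protocol 3.6.2.5 repeats the rule for one source of findings: "Clinically significant changes from screening/baseline in the physical examination for a surgical or medical patient will not be recorded as AEs", with the same proviso. SAP 6.3.6 has no such proviso: "changes from screening/baseline in the physical examination will be recorded as AEs".

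On conventional opioids, Protocol 1.1 says "their use is hampered by well-known adverse events (AEs), such as respiratory depression, nausea, vomiting, and sedation". The same section lists nausea, dizziness, vomiting and headache as the commonest phase 2 events with oliceridine.

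Protocol 4.2.1 adds: "All AEs must be recorded irrespective of whether they are considered medication-related".

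**The concern.** Nausea, vomiting and drowsiness are common after surgery and are also effects of the drug class. When such an event of ordinary severity follows a dose, the investigator must first decide whether it was to be expected from the operation or illness. If so, it is never entered. That is in effect a causality judgment made before recording. It is made by someone who knows that every patient receives oliceridine, and it leaves no trace in the AE data. The general definition earlier in 4.1.1 takes the opposite approach: a new event counts whether or not the drug is thought responsible.

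An event that is not entered drops out of every TEAE table, including the table of events seen in at least 5% of patients. There is no control arm in which the same under-recording would show. If the rule is also applied in some settings and not in others, the by-setting table shows differences that come from recording practice.

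**Working it through.** The plan gives no figure to reproduce: about 1000 patients, no sample-size calculation, no precision target. The check has a textual part and an illustrative part.

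**Can the named opioid effects be called anticipated?** In the abdominoplasty phase 2 study (Protocol 1.1), the placebo group had 18% nausea, 8% vomiting and 10% hypoventilation. The two oliceridine regimens had 41% and 46% nausea, 15% and 15% vomiting, and 15% and 31% hypoventilation. These events occur after surgery without the drug and more often with it. Nothing in 4.1.1 stops an investigator from treating them as expected.

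**What else captures them during dosing?**
- Sedation: Moline-Roberts scale, tabulated by level.
- Blood pressure, pulse, oxygen saturation: summarized over time, with threshold counts (SAP 6.3.4, 6.3.8).
- Respiratory rate: summarized over time, but with no threshold criterion in SAP 6.3.4.
- Nausea, vomiting, dizziness, headache: no parallel measure. The withdrawal scale has nausea and vomiting items but is given one day after treatment (SAP 6.3.7).
- Physical examination: SAP 8.6.6 plans only a listing, so AE entries are the main route into tables.

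**Who is covered?** Exclusion criterion 4 and the footnotes to the Schedule of Events set surgical or medical patients apart from ED patients, and SAP 6.2.2 uses Surgical, Medical and ED as three settings. On that usage the exemption omits ED patients. The synopsis, however, describes the whole study as one in surgical and medical patients and includes EDs in the same sentence.

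**Illustration of size.** Let p be the true incidence (phase 2 rates above) and f the share of true events left unrecorded. The documents give no value for f; the range here is assumed. Recorded incidence = p × (1 − f).

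| True rate p | f = 0 | f = 0.10 | f = 0.25 | f = 0.50 |
|---|---|---|---|---|
| Nausea 46% | 46% | 41.4% | 34.5% | 23.0% |
| Nausea 41% | 41% | 36.9% | 30.75% | 20.5% |
| Vomiting 15% | 15% | 13.5% | 11.25% | 7.5% |

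If ED patients are outside the rule and have the same true rate, the artificial gap between settings is p × f. For 46% nausea that is 4.6, 11.5 and 23.0 points at f = 0.10, 0.25 and 0.50.

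For scale, the 95% half-width with 1000 patients is 1.96 × √(p(1 − p)/1000). At 46% it is 1.96 × √(0.46 × 0.54/1000) = 3.1 points, so the bias exceeds sampling error once f passes 0.031/0.46, about 0.07. At 15% it is 2.2 points, and the crossing point is 0.022/0.15, about 0.15. Both take the rule as applying to all 1000 patients; with ED patients outside it, the overall bias is diluted in proportion to their share.

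**The case against.** The best defence is that the sentence means only the expected symptoms of the operation or illness, such as wound pain. The documents nowhere call nausea or sedation anticipated for a surgical patient; they name them as opioid AEs, and investigators must know the brochure. That reading is sensible and close to the fix below. But it is not written down, and sites may not all adopt it.

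Several stronger readings that a reader might infer are not supported:
- **A full exemption.** The rule is a threshold: symptoms worse than expected are recorded.
- **A contradiction with Protocol 4.2.1.** That sentence concerns causality and presupposes the definition in 4.1, so a narrower definition does not contradict it.
- **ED patients certainly recorded under another rule.** This is the literal reading, but the synopsis makes it ambiguous, and no text says that anticipated symptoms in ED patients must be entered.
- **Total loss of information.** Besides the parallel measures above, Protocol 4.1.3 makes clinically significant abnormal assessments reportable (again by judgment), and the medication listing gives indication and any linked AE, so treated nausea leaves a trace.
- **A like-for-like comparison of settings spoiled by this rule alone.** The settings also differ in case mix, and SAP 7.7 rules out testing.

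The phase 2 rates are only a guide. That study used PCA demand doses of 0.1 and 0.35 mg against 0.5 mg here, and its AE recording rule is not stated.

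**Conclusion.** The point holds as a risk of understatement, not as a demonstrated bias. As written, the rule can only lower recorded TEAE incidence, and nothing in the plan protects the effects of most interest. The exposure is mainly nausea, vomiting, dizziness and headache of ordinary severity, especially when untreated.

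The direction follows from the text; the size does not. Every figure other than f = 0 rests on an assumed f and on borrowed phase 2 rates, and at f = 0 there is no bias. What can be said is that for an event as common as nausea, a loss of roughly one event in fourteen (about 7%) would already exceed the sampling error of the whole study.

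For settings, the conclusion is that a descriptive table may mix recording rules, not that the settings are shown to be non-comparable. The conflict between Protocol 3.6.2.5 and SAP 6.3.6 needs no assumption: the two cannot both be followed.

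**What to change.** 1. In Protocol 4.1.1 and 3.6.2.5, limit the exemption to symptoms or findings of the qualifying surgery or condition, for example surgical-site pain.
2. State that after the first dose it does not apply to effects the protocol already lists for the drug or class: nausea, vomiting, dizziness, headache, somnolence or sedation, hypotension and respiratory signs. These are entered whatever their severity; the relationship field then carries the causality view.
3. State that one rule applies to surgical, medical and ED patients alike.
4. Reconcile SAP 6.3.6 with Protocol 3.6.2.5 so that both give the same rule for examination changes.

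The cost is an amendment of wording, a notice to sites, more AE entries and a somewhat higher reported incidence. The documents do not say whether enrolment has begun. If it has, events recorded before and after the change should be flagged and the main TEAE tables shown for both periods, because the database would then hold two recording rules.
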